6.3.3 Dose modifications Siltuximab

Table 9. Dose reduction steps for siltuximab

Overall, patients with AEs suspected to be related to siltuximab include pruritus, increased weight (edema), rash, hyperuricemia, and upper respiratory tract infection. Rare side effects include gastrointestinal perforation.

Each patient can receive a maximum of 2 dose reductions of siltuximab prior to permanent discontinuation of siltuximab.

Siltuximab can be held for a maximum of 12 weeks, if no resolution of toxicity to grade 1 or less, then siltuximab will be permanently discontinued.

Dose reduction*											
Starting dose level – 0 Dose level – 1 Dose lev											
Siltuximab	11 mg/kg	9 mg/kg	6 mg/kg **								
*Dose reduction should be based on the worst toxicity demonstrated at the last dose.											
**Dose reduction below 6 mg/Kg is not allowed.											

- 1. Weight gain due to edema **grade 1 or 2** manage symptomatically with diuretics. Patients with **grade 3** hold siltuximab treat symptomatically resume at one dose level lower once grade 1. Patients with **grade 4** hold siltuximab and treat symptomatically. Permanently discontinue siltuximab for first occurrence of grade 4 weight gain.
- 2. Hyperuricemia grade 1 or 2 continue treatment with siltuximab and monitor. Grade 3 start therapy for hyperuricemia (allopurinol) and hold siltuximab until it resolves to grade 1. Resume at a lower dose level. Grade 4 hold siltuximab permanently, treat hyperuricemia (rasburicase).

Protocol/Version No.: 5, Date December 15, 2022

3. Upper respiratory tract infection grade 1 and 2 treat infection and continue siltuximab. Grade 3 or 4 hold siltuximab treat infection. First occurrence of grade 4 upper respiratory tract infection will lead to permanent discontinuation of siltuximab. For Grade 3, resume after infection treated no dose reduction for first occurrence. Dose reduce by one dose level for second occurrence. Hold permanently for third occurrence.

- 4. Pruritus grade 1 and 2 treat symptomatically and continue siltuximab. Grade 3 hold siltuximab, treat symptomatically, resume siltuximab after symptoms resolve.
- 5. Gastrointestinal perforation any grade permanently hold siltuximab.
- 6. Dose modifications of siltuximab for hematologic and non-hematologic toxicities also review 6.3.2.2.

6.3.4 Timing of Dose Administration

Trial treatment should be administered on Day 1 of each cycle after all procedures/assessments have been completed as detailed. Trial treatment may be administered up to 3 days before or after the scheduled Day 1 of each cycle due to administrative reasons.

All trial treatments will be administered on an outpatient basis.

Spartalizumab 300 mg will be administered as a 30 minute IV infusion every 3 weeks. Given the variability of infusion pumps, a window of -5 minutes and +10 minutes is permitted (i.e., infusion time is 30 minutes: -5 min/+10 min).

Siltuximab will be administered IV infusion over a period of 1 hour on day 1 of every 3-week cycle. Given the variability of infusion pumps, a window of -10 minutes and +10 minutes is permitted (i.e., infusion time is 60 minutes: -10 min/+10 min).

The Pharmacy Manual contains specific instructions for the preparation of the spartalizumab and siltuximab infusion fluid and administration of infusion solution.

6.3.5 Trial Blinding/Masking

This is an open-label trial; therefore, the Sponsor, investigator and subject will know the treatment administered.

6.4 Concomitant Medications/Vaccinations (allowed & prohibited)

Medications or vaccinations specifically prohibited in the exclusion criteria are not allowed during the ongoing trial. If there is a clinical indication for one of these or other medications or vaccinations specifically prohibited during the trial, discontinuation from trial therapy or

Protocol/Version No.: 5, Date December 15, 2022

vaccination may be required. The investigator should discuss any questions regarding this with the PI. The final decision on any supportive therapy or vaccination rests with the investigator and/or the subject's primary physician.

6.4.1 Acceptable Concomitant Medications

All treatments that the investigator considers necessary for a subject's welfare may be administered at the discretion of the investigator in keeping with the community standards of medical care. All concomitant medication will be recorded on the case report form (CRF) including all prescription, over-the-counter (OTC), herbal supplements, and IV medications and fluids. If changes occur during the trial period, documentation of drug dosage, frequency, route, and date may also be included on the CRF.

All concomitant medications received within 28 days before the first dose of trial treatment and 30 days after the last dose of trial treatment should be recorded. Concomitant medications administered after 30 days after the last dose of trial treatment should be recorded.

In general, concomitant medications and therapies deemed necessary for the supportive care (e.g. such as anti-emetics, anti-diarrhea) and safety of the patient are allowed.

- Medications to prevent or treat nausea or vomiting.
- Anti-diarrheal medications (e.g., loperamide) for patients who develop diarrhea.
- Pain medication to allow the patient to be as comfortable as possible.
- Treatment with bisphosphonates or denosumab for pre-existing, painful bone/liver metastases, and limited-field palliative radiotherapy or surgery is permitted. Patients requiring initiation of such treatment during the course of the study must be evaluated for disease progression; radiotherapy like any concomitant medication must be listed on the CRF. Spartalizumab and siltuximab should be held for ≥1 week prior to radiotherapy or surgery, and be resumed ≥2 weeks after radiation or surgery, provided the patient has recovered from radiation or surgery related toxicity.
- Immunosuppressive agents to treat suspected irAEs
- Hematopoietic colony-stimulating growth factors (e.g. G-CSF, GM-CSF, M-CSF), thrombopoietin mimetics or erythroid stimulating agents as per local or published guidelines; in case of anemia, thrombocytopenia or neutropenia, potential immunemediated etiology should be ruled out
- Nutritional support or appetite stimulants (e.g. megestrol).
- Oxygen therapy and blood products or transfusions.
- Inactivated vaccines.
- The patient must be told to notify the investigational site about any new medications he/she takes after the start of the study drug. All medications (other than study drug) and significant non-drug therapies (including physical therapy, herbal/natural medications and

Protocol/Version No.: 5, Date December 15, 2022

blood transfusions) administered during the study must be listed on the Concomitant Medications.

6.4.2 Prohibited Concomitant Medications

During the course of the study, patients must not receive other antineoplastic therapies (e.g. investigational drugs, devices, chemotherapy, immunotherapies) or any other therapies that may be active against cancer or modulate the immune responses. However, limited-field palliative radiotherapy may be allowed as concomitant therapy (see above).

The use of systemic steroid therapy and other immunosuppressive drugs is not allowed except for the treatment of infusion reaction, irAEs, and for prophylaxis against imaging contrast dye allergy, standard pre-medication for chemotherapy or replacement-dose steroids in the setting of adrenal insufficiency (providing this is < 10 mg/day prednisone or equivalent), or transient exacerbations of other underlying diseases such as COPD requiring treatment. If systemic corticosteroids are required for the control of infusion reactions or irAEs, it must be tapered and be at non-immunosuppressive doses (< 10 mg/day of prednisone or equivalent) before the next administration of study treatment. If the dose of prednisone or equivalent cannot be reduced to less than 10 mg/day before the administration of next dose of study treatment then spartalizumab or siltuximab must be discontinued (note: next dose can be delayed up to 12 weeks).

The use of live vaccines is not allowed through the whole duration of the study. Inactivated vaccines are allowed.

There are no prohibited therapies during the post-treatment follow-up period except for live vaccines within 4 weeks of last administration of siltuximab.

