6.3.2 Dose modification and dose interruption for spartalizumab and siltuximab

General dose modification instructions:

Siltuximab and spartalizumab have class-specific safety profiles based on their mechanism of action but may also cause AEs that overlap. For management of AEs which can be clearly attributed to siltuximab or spartalizumab, independent dose modification for either agent is allowed. For AEs without clear attribution to either study treatment, management of toxicity should include dose modifications of both agents.

Overall AEs are to be graded according to NCI-CTCAE v4.03 (http://ctep.cancer.gov). All dose interruptions and the reason for the dose interruption must be documented in the eCRF.

Overall, patients with AEs suspected to be related to *spartalizumab* including those of potential immune-mediated etiology (irAE) may need to interrupt or permanently discontinue spartalizumab as outlined in Section 6.3.2. In general, study treatment with spartalizumab must be permanently discontinued in case of:

- Any life-threatening adverse reactions (excluding endocrinopathies controlled with hormone replacement therapy)
- Persistent Grade 2 or 3 adverse reactions (excluding endocrinopathies controlled with hormone replacement therapy) that do not recover to <= Grade 1 within 12 weeks after last dose of study treatment
- Inability to reduce the dose of steroids (for the management of irAE) to 10 mg/day or less of prednisone or equivalent (or as indicated in the tables below) within 12 weeks
- Any severe or Grade 3 recurring treatment-related adverse reaction

The 12 weeks' timeframe will begin from the time the irAE reaches a grade that leads to spartalizumab interruption.

Overall, patients with AEs suspected to be related to *siltuximab* include pruritus, increased weight (edema), rash, hyperuricemia, neutropenia, and upper respiratory tract infection. Rare side effects include gastrointestinal perforation. Toxicities may require interruption of therapy,

Protocol/Version No.: 5, Date December 15, 2022

dose reduction or permanent discontinuation from trial as detailed in section 6.3 and Tables 8-8 and 8-9. In general study treatment with siltuximab must be discontinued for:

- Gastrointestinal perforation
- Grade 4 weight gain
- Grade 4 upper respiratory tract infection
- Recurrent or severe grade 3 treatment-related adverse events.
- Life threatening adverse events
- Interruption of therapy for longer than 12 weeks

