other clinical sequelae (e.g., renal impairment, pulmonary infiltrates) Grade 4: Life-threatening; pressor or ventilatory support indicated	 Acetaminophen Narcotics Oxygen Pressors Corticosteroids Epinephrine Increase monitoring of vital signs as medically indicated until the patient is deemed medically stable in the opinion of the investigator. Hospitalization may be indicated. 	

2nd occurrence of grade 2 irAE (including colitis/diarrhea, LFT abnormalities, rash, nephritis and other AEs as listed in table 8-6) or for grade 2 irAE lasting more than 12 weeks. Permanently discontinue spartalizumab.

6.3.2.1.2 Guidance for corticosteroids tapering for management of immune-related AEs:

Steroids should be tapered slowly and based on response/recovery of clinical symptoms. Consider to complete tapering over a period of at least 4 weeks. Slower tapering of corticosteroids therapy may be recommended if the adverse event is not showing improvement.

Protocol/Version No.: 5, Date December 15, 2022

Once corticosteroid tapering is achieved at a level of 10 mg of prednisone/day (or equivalent), spartalizumab can be restarted as indicated in the dose modification tables.

6.3.2.2 Dose modification requirements for adverse events suspected to be related to study treatment

The required dose modification and management of adverse events that are considered to be related to study medication and do not have specific management requirements noted elsewhere in the protocol are provided in Table 8-8 & Table 8-9.

Table 8-8 Mandatory dose modification requirements and recommended clinical management guidelines for hematologic adverse events suspected to study treatment

Hematologic su	spected AEs (NCI-CTCAE v4.03)	
Grade	Recommended Adverse Event management guidelines	Mandatory Dose Modification requirements
Neutropenia		
Grades 1, 2	NA	Continue spartalizumab and siltuximab

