Grade 3, 4	Monitoring blood test more frequently (every 7 days for grade 3, and 3-5 days for grade 4) Consider consulting with a specialist, initiation of corticosteroids or other therapies as medically appropriate and as per institutional guidelines.	1st occurrence: Interrupt spartalizumab and siltuximab until toxicity recovers to Grade ≤2 or baseline. Once recovered restart spartalizumab and siltuximab treatment at the same dose and schedule Grade 4 febrile neutropenia or thrombocytopenia should lead to permanent discontinuation of spartalizumab and siltuximab 2nd occurrence: Interrupt spartalizumab and siltuximab until toxicity recovers to Grade ≤2 or baseline Once recovered restart spartalizumab and siltuximab treatment at the same dose and schedule
		AE resolution to ≤ Grade 2 or baseline must occur within a maximum period of 12 weeks since Grade 3 or 4 event has been identified, otherwise spartalizumab

Grade	Recommended Adverse Event management guidelines	Mandatory Dose Modification requirements
		and siltuximab must be permanently discontinued
		3 rd occurrence:
		Permanently discontinue spartalizumab and siltuximab
Febrile Neutropenia	Apply Institutional guidelines	Follow- neutropenia Grade 4 requirements (above)
Thrombocytopeni	ia (NCI-CTCAE v4.03)	
Grade 1, 2, 3 without clinical significant bleeding	Grade 3: monitoring blood test more frequently (every 7 days)	Continue spartalizumab and siltuximab
Grade 3 with	Monitoring blood test more frequently	1 st occurrence:
clinical significant bleeding OR Grade 4	(every 3-5 days) Consider consulting with a specialist, initiation of corticosteroids or other therapies as medically appropriate and as per institutional guidelines.	 Interrupt spartalizumab and siltuximab until toxicity resolves to Grade ≤2 or baseline. Once recovered restart spartalizumab and siltuximab at the same dose and schedule
		2 nd occurrence:
		 Interrupt spartalizumab and siltuximab until toxicity resolves to Grade ≤2 or baseline Once recovered restart spartalizumab and siltuximab at the same dose and schedule
		AE resolution to ≤ Grade 2 or baseline must occur within a maximum period of 12 weeks since Grade 3 with clinically significant bleeding or Grade 4 event has been identified, otherwise spartalizumab and siltuximab must be permanently discontinued.
		3 rd occurrence:
		permanently discontinue spartalizumab and siltuximab

Protocol/Version No.: 5, Date December 15, 2022

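### The 12-week rules for stopping or restarting treatment disagree on the steroid level, the start of the clock and the recovery grade

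*Combined protocol and SAP*

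**What the plan says.** **Steroid level.** The general list in 6.3.2 makes permanent discontinuation of spartalizumab depend on "Inability to reduce the dose of steroids (for the management of irAE) to 10 mg/day or less of prednisone or equivalent" within 12 weeks. Section 6.3.2.1.2 agrees: "Once corticosteroid tapering is achieved at a level of 10 mg of prednisone/day (or equivalent), spartalizumab can be restarted". Section 6.4.2 sets a strict limit. It first requires a taper to below 10 mg/day before the next administration, then continues: "If the dose of prednisone or equivalent cannot be reduced to less than 10 mg/day before the administration of next dose of study treatment". In that case it calls for stopping one or other drug, after a permitted delay of at most 12 weeks.

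**Clock.** In the same 6.3.2 list, spartalizumab stops for Grade 2 or 3 reactions "that do not recover to <= Grade 1 within 12 weeks after last dose of study treatment". The sentence after the list reads "The 12 weeks' timeframe will begin from the time the irAE reaches a grade that leads to spartalizumab interruption". Table 8-8 (hematologic) and Table 8-9 (non-hematologic, immune-related events excluded) count from identification of the event.

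**Recovery grade.** The 6.3.2 bullet requires Grade 1 or less. For siltuximab, the stopping rule in 6.3.3 begins "Siltuximab can be held for a maximum of 12 weeks, if no resolution of toxicity to grade 1 or less, then siltuximab will be permanently", and it ends with discontinuation. Table 8-8, for interrupted neutropenia, says "AE resolution to ≤ Grade 2 or baseline must occur within a maximum period of 12 weeks since Grade 3 or 4 event has been", with the count running from identification. It has a parallel rule for thrombocytopenia and restarts both drugs once that level is reached.

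The text before Table 8.0 makes the dose modification requirements mandatory and only the management guidance advisory.

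**The concern.** These passages answer one question: when does a persisting toxicity end treatment? They give different answers for the same clinical course. Permanent discontinuation of one drug generally ends the other under 6.3.2, although patients with CR, PR or SD may continue on a single agent and siltuximab may continue for control of immune-related events. The decision feeds the disposition table (12.4), the summary of adverse events leading to discontinuation (12.5.1.1) and the dose-modification summary (12.5.1.3). If sites apply different sections, those outputs partly reflect which section was read.

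**Working it through.** The plan states no figure to reproduce. The check compares the passages at their boundaries and adds date arithmetic, with 12 weeks = 84 days.

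**1. Steroid level at the end of the allowance**

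| Prednisone, mg/day | 6.3.2 stops (above 10) | 6.3.2.1.2 permits restart (10 or less) | 6.4.2 stops (not below 10) |
|---|---|---|---|
| 9.9 | no | yes | no |
| 10 | no | yes | yes |
| 10.1 | yes | no | yes |

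The sections part only at exactly 10 mg/day, which is the level that 6.3.2.1.2 itself names. Before the 12 weeks end, 6.4.2 lets the next dose wait, so the conflict over stopping arises when the allowance runs out.

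**2. Clock.** Let the event be identified k days after the last dose.

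- Last-dose clock (6.3.2 bullet): ends on day 84.
- Event clock (Tables 8-8 and 8-9): ends on day 84 + k.
- Recovery between day 85 and day 84 + k is too late on the first clock and in time on the second: a window of k days.

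| k | Last-dose clock ends | Event clock ends | Window, days | Share of 84 days |
|---|---|---|---|---|
| 7 | 84 | 91 | 7 | 8% |
| 14 | 84 | 98 | 14 | 17% |
| 21 | 84 | 105 | 21 | 25% |
| 24 | 84 | 108 | 24 | 29% |

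The interval is 21 days, or 24 if the next dose is 3 days late (6.3.4). A dose 3 days early followed by one 3 days late gives 27 days (27/84 = 32%).

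Example: a Grade 3 non-hematologic event that is not immune-related is identified on day 20 and recovers to Grade 1 on day 95. From identification, 95 − 20 = 75 days, which is within 84, so Table 8-9 restarts both drugs. From the last dose it is 95 days, which exceeds 84, so 6.3.2 permanently stops spartalizumab.

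Further 12-week limits on a hold or delay, in 6.2, the siltuximab list of 6.3.2, 6.3.3 and 6.4.2, give no start point.

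**3. Recovery grade, for a cytopenia that Table 8-8 interrupts, at week 12**

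| Grade | Table 8-8 | 6.3.2 and 6.3.3 |
|---|---|---|
| 1 | restart | no stop |
| 2 | restart | permanent stop |
| 3 | no restart (unless this is baseline) | permanent stop |

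If Grade 2 is reached well before week 12, Table 8-8 restarts at once while 6.3.3 implies a continued hold. Once dosing resumes, the hold is over and a new last dose resets the 6.3.2 count. Restart against permanent stop therefore needs Grade 2 to be first reached near week 12.

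**4. DLT window.** The DLT period is 6 weeks (42 days), and the expansion stopping rule in 12.1 looks at 8 weeks (56 days). Even for an event on the day of the first dose, a full 12-week allowance expires no earlier than day 84: 84 − 42 = 42 days after the first window and 84 − 56 = 28 days after the second.

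**5. Size in the tables.** The documents give no expected frequency for these events. With 27 to 42 treated patients, one patient classified differently moves a discontinuation percentage by 1/27 = 3.7 to 1/42 = 2.4 points.

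**The case against.** The strongest reply is that these are boundary differences and that the protocol signals how to read them.

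- **Steroids.** Section 6.3.2.1.2 only permits restart, so a site that always tapers below 10 mg/day complies with all three sections. This stands: the conflict is permission to restart against an obligation to discontinue, at a single dose level. But nothing tells a site that restarts at 10 mg/day under 6.3.2.1.2 that 6.4.2 overrides it.
- **Clock.** For immune-related events, the sentence closing the 6.3.2 list sets an onset-based start, close to the one in the tables. This largely settles those events. It does not reach Table 8-9, which excludes them, or other events handled under Table 8-8.
- **Grade.** The 6.3.2 lists are introduced as general, the steroid bullet defers to the tables, and 6.3.2 and 6.3.3 point to Tables 8-8 and 8-9 or to 6.3.2.2. A reader may infer that the specific table governs. That is plausible, but the cross-reference in 6.3.3 only asks for 6.3.2.2 to be reviewed as well, and no order of precedence is stated.

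A reader might also infer that every Grade 3 or 4 cytopenia settling at Grade 2 is affected. It is not. Table 8-8 continues dosing through Grade 3 thrombocytopenia without clinically significant bleeding, and its neutropenia entry separately directs permanent discontinuation for Grade 4 febrile neutropenia or thrombocytopenia.

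**Conclusion.** The inconsistency is real and should be corrected, within limits. The steroid conflict exists only at exactly 10 mg/day when the allowance ends. The clock conflict applies to events that are not immune-related and spans up to about 3 of 12 weeks, assuming dosing was on schedule before the event. The grade conflict applies to cytopenias that Table 8-8 interrupts: restart against continued hold, becoming restart against permanent stop only near week 12.

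Two stronger readings are not supported. One is that the same patient must always be both restarted and permanently stopped: the steroid passages do not oblige anyone to restart, and the other two conflicts need the timing shown above. The other is that dose escalation is compromised because Table 7 counts an adverse event leading to permanent discontinuation as a DLT. A 12-week outcome normally falls after the 6-week window, and the protocol does not say that a later stop is counted back to the event's onset.

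What remains is an effect on exposure, treatment discontinuation and the descriptive safety summaries. No sample size, power or error rate changes.

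**What to change.** Reconcile 6.3.2, 6.3.2.1.2, 6.3.3, 6.4.2 and Tables 8.0 to 8-9 so that the following are the same throughout:

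- one steroid threshold, stated as either at or below, or strictly below, 10 mg/day;
- one start of the 12-week clock, applied also to the hold and delay limits that now have none;
- one recovery grade for each event class.

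Add a sentence saying which text prevails where the general list and a table differ. Which threshold, clock and grade to adopt is the sponsor's clinical decision.

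The cost is a wording amendment. Sample size and planned analyses are unchanged. If any patient has already been managed at one of these boundaries, the report should state which section was applied.
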